## Sample Size Information

### 1.0 Complete the table below to reflect the minimum number of human subjects required to complete this research:

- \* Proposed overall sample size: 300
- \* Proposed local sample size: 105

### 2.0 If applicable, provide a statistical sample size justification stated in terms of study power or confidence interval width.

Our power analysis is based on our primary hypothesis that the Mentoring Program will provide a significantly greater increase in QOL compared to the Educational Activity group from baseline to post-treatment. We use a Type I error rate of .05 to test this primary hypothesis. For examining statistical power, we assume an independent samples t-test is used to test this hypothesis with a minimum of 80% power to obtain a sufficient per group sample size ( $n$ ), which is assumed equal across groups. Consequently, the standardized mean difference is the effect size required to obtain power and sample size. Our primary analysis also allows for the inclusion of site, gender and the baseline measure of the outcome as covariates, which will allow for an  $n$  equal to or smaller than that reported here for the same level of statistical power.

The results of our pilot study are used to estimate effect size for our power analysis. We found a standardized mean difference of .52 on the QOL total scale when examining group differences in pre-post change. We found effect sizes of .52 and 1.08 on the functional disability score and on the QOL social scale respectively, thus generally illustrating that we should expect effect sizes in the medium to large range for the current R01. Our sample size of n=100 per group (mentoring vs. comparison) would provide 94% power for a medium effect size of d=.5 and more than 99% power to detect a large effect size of d=.8. Even with 20% attrition, we would still have 88% power to detect a medium effect size and over 99% power to detect a large effect size. Thus, our sample size of n=100 is sufficient for detecting treatment effects that we would expect.

## Special Subjects Population

### 1.0 \* Check all that apply to describe your study population:

Study Population

**Children or Adolescents (minors)**

Pregnant Women or Fetuses

Fetal Tissue

Adults Who May Lack Capacity to Consent

Employees or Students of the Investigators

**Patients of the Investigators**

Other Patients from CCRI or other Institution

Prisoner

Economically Disadvantaged

Non-English Speaking

Not Applicable

### 2.0 If any of the above are selected, describe additional safeguards included in the protocol to protect the rights and welfare of these special populations:

Informed consent from parents and assent from youth will be obtained from all participants prior to beginning any study procedures. No one will participate unless both consent and assent are given. They will be given time to ask questions and to consider whether or not to participate. Consent and assent forms are written in language understandable to parents and children. Since some of the participants may be patients of the investigators, all study staff will be trained in procedures to minimize the possibility of coercion or undue influence.

## Minor Subjects

### 1.0 \* Please check one box below that is most applicable to your research:

Child Category

Level 1 - Research not involving greater than minimal risk.

**Level 2 - Research involving greater than minimal risk but presenting the prospect of direct benefit to the individual**

Level 3 - Research involving greater than minimal risk and no prospect of direct benefit to individual, but likely to yield generalizable knowledge about the subject's disorder or condition.

Level 4 - Research not otherwise approvable which presents an opportunity to understand, prevent or alleviate a serious problem affected the health or welfare of children.

### 2.0 \* Please discuss your rationale for the classification you have chosen above in Question 1:

There is a risk of loss of confidentiality, since participants will be engaging in group activities with other participants. There is risk for emotional or physical harm for mentees participating in the Mentoring Program. Another potential risk is that of cost for those participating in the Mentoring Program. Participants will be reimbursed for data collection, but not for participating in the Mentoring Program itself. Finally, there is a risk that the web-based components (e.g., program

website) could be "hacked" and sensitive information accessed. However, there is the prospect of direct benefit: Participants in the program may experience improved self-management, quality of life and functional ability.

**3.0 \* Describe how you will obtain both parental permission and the minor's assent for the minor to participate in the research:**

Consent and assent will be obtained before completion of any questionnaires. Study personnel will explain the purpose of the study and procedures in simple language. All questions will be answered. Parents and mentors >18 years old will sign consent forms and all youth will sign assent forms. Any participant who has turned 18 years old during the course of this longitudinal study will sign a consent form at the next opportunity after his or her birthday (e.g., group event or post-intervention study visit).

## Finding Subjects

**1.0 \* Please check the box(es) below that best reflect how patients will be identified and recruited for participation.**

How subjects will be identified

- Potential subjects will self-refer in response to advertisements.**
- Subjects will roll-over from another research study.
- Potential subjects will be identified from a registry of individuals interested in research opportunities.**
- Medical records and/or other Institution sources (databases, billing records, pathology reports, admission logs, etc.) will be reviewed to identify potential participants. May involve access of records by individuals not involved in the patient's care.**
- Potential subjects will be identified by their treating physicians and referred to the researchers. Patients' private and identifiable information will not be shared prior to receiving permission from the patient to do so.**
- Potential subjects will be identified and approached during an inpatient or outpatient clinical visit by a member of the research team**
- Other**

**2.0 \* Do you assure the IRB that you acknowledge the need to address the potential for coercion and that you will employ reasonable and appropriate steps to emphasize the voluntary nature of participation?**

Yes  No

## Informed Consent

**1.0 \* Check one box below to indicate whether informed consent will be obtained or whether you are requesting a waiver of the requirement for informed consent or documentation of informed consent:**

Informed Consent Category

- Subjects will be asked to sign a study consent form after receiving a complete explanation of the study.**
- Subjects will receive a complete explanation of the study and will be asked to consent verbally.
- Subjects may receive a written summary of the research as outlined in the attached written Study Information Sheet. Subjects will not be asked to sign a consent form. (Waiver of Documentation of Consent)
- Subjects will not be asked to consent to participation. A waiver of the requirement for written and verbal informed consent is requested.
- Consent to collect and analyze the samples and/or data to be used for this research was/will be obtained under a separately approved protocol. The analysis to be done falls within the parameters of the consent originally provided by the participant.

## Informed Consent Process

### 1.0 \* Who will obtain informed consent from subjects for this research?

Study personnel who have been trained in consent procedures.

### 2.0 \* Describe how, when, and where the consent process will be initiated:

All participants will be consented prior to the initiation of any study procedures.

Youth: Adolescents with IBD will be consented prior to the initial study visit, either in clinic or immediately prior to collecting baseline data.

Mentors: Mentors will participate in a 2-step consent process. The first consent is for the online mentor application (which serves as the baseline data collection). Then, if they are accepted into the program as a mentor, they will provide consent for the mentoring program and post-intervention data collection.

The application/baseline data collection for mentors will be completed on a secure website (REDCap). Interested applicants will contact study staff who will then give them the link for the website via secure email. For applicants  $\geq 18$  years old, they will provide consent on the website. For applicants who are 16 – 17 years old, study staff will first discuss the study with them and their parents via phone or in clinic, send/give parents the consent forms, and the parents will send/give signed consent forms back to us. After we receive the signed consent forms from the parent, we will give the applicant the link for the website. The consent process on the website will serve as assent for these participants.

Applicants who pass the screening process and wish to participate in the mentoring program as a mentor will provide consent to do so when we meet with them prior to introducing them to a mentee. For mentors who are 16 – 17 years old, study staff will send their parents this consent form and answer any questions via phone. Parents will send the signed consent form back, or the mentor will bring it with him/her when we meet. The mentor will sign an assent form at this time.

### 2.1 Describe any waiting period between informing the prospective subject and obtaining consent:

N/A

### 2.2 \* Describe the steps taken to minimize the possibility of coercion or undue influence:

Potential participants will be informed that they may refuse to be in the study or quit the study at any time, and standard medical care will still be available without a penalty or loss of benefits to them.

### 2.3 \* Who will give consent or permission for this research? (Ex. Parent, Self, Legal Guardian):

Adult participants and the parent or legal guardian of minor participants will sign consent forms for this research. Adolescents will provide assent for this research.

### 3.0 \* Do you plan to include subjects who do not speak English?

Yes  No

\*If 'Yes', answer 3.2; if 'No', answer 3.1

### 3.1 If Non-English speaking subjects will be excluded, provide a scientific rationale for their exclusion:

Not all questionnaires have been validated in other languages.

### 3.2 If Non-English speaking subjects will be included, check all that apply to describe how consent will be obtained and documented:

Translation Method

- 
- A complete translation of the approved English consent form will be submitted to the IRB.
- Not anticipated. Will contact the IRB if necessary for short form guidance.
- 

### 3.3 If Non-English speaking subjects will be enrolled, describe the translation services available for the conduct of the consent process and the conduct of the research:

**4.0 Consent Forms - Approved:**

Name	Version
CCHMC adult mentor program consent.doc	0.01
CCHMC Minor Mentor APP Consent.docx	0.01
CCHMC Minor Mentor PROGRAM Assent.doc	0.01
CCHMC Minor Mentor PROGRAM Consent.docx	0.01
CCHMC Youth Assent.doc	0.01
CCHMC Youth Consent.docx	0.01
CHW adult mentor program consent.doc	0.01
CHW Minor Mentor APP Consent.docx	0.01
CHW Minor Mentor PROGRAM Assent.doc	0.01
CHW Minor Mentor PROGRAM Consent.docx	0.01
CHW Youth Assent.doc	0.01
CHW Youth Consent.docx	0.01
R01 adult mentor program consent.doc	0.01
R01 Minor Mentor APP Consent.docx	0.01
R01 Minor Mentor PROGRAM Assent.doc	0.01
R01 Minor Mentor PROGRAM Consent.docx	0.01
R01 Youth Assent.doc	0.01
R01 Youth Consent.docx	0.01

**Inclusion and Exclusion Criteria****1.0 \* List the specific study inclusion criteria:**

Youth: Age 10 – 17 years with diagnosis of IBD

Mentors: Age 16-35 years, ≥1 year post-diagnosis, and pass screening process including a written application, background check, sex offender, social media, and child abuse registry check, interview, and character references

**2.0 \* List the specific study exclusion criteria:**

- (1) Documented neurodevelopmental disorder, or
- (2) History of hospitalization for a psychiatric or behavioral disorders, or
- (3) Documented significant behavioral/emotional problems that would interfere with appropriate participation in the program, for example, behavioral/emotional problems that would interfere with group activities and/or would be beyond the scope of the training and supervision provided to mentors.

**3.0 \* Will participation in the research be limited to individuals who meet specific criteria related to age, gender, race, preferred language or any other demographic or socio-economic condition:**

Yes

**4.0 If you answered yes to question 3, please provide a justification for the limitations on enrollment of subjects:**

The study is designed to look at the adolescent population, when many patients are often diagnosed and when self-management is often a challenge. Therefore age is limited due to aims of study.

## Benefits and Risks

### 1.0 \* Describe the potential benefits (physical, psychological, social, or other) that may be gained by the subject, as well as by society in general:

Participants may experience improved self-management in the areas of QOL and functional ability via improved self-efficacy, illness uncertainty, coping, and social support.

### 2.0 \* Risks - Describe and assess any potential risks (physical, psychological, social, legal, financial or other) and assess the likelihood and seriousness of such risks. If methods of research create potential risks, describe other methods, if any, that were considered and why they will not be used:

Questionnaire data collection

It is feasible that some of the questions could cause some distress or anxiety, but it is unlikely to have severe or long-lasting effects on the respondent.

Loss of confidentiality

A mentoring program by its very nature imposes some limits on confidentiality as mentors and mentees are expected to share personal information. Participants will also be engaging in group activities with other participants. The risk is that this private information will be shared with others outside of the mentoring relationship or group activity. For our R21 proposal, we realized that the likelihood of this risk of unintentional or unwanted disclosure was difficult to determine, so our program coordinator currently asks about confidentiality concerns during her "check-in" calls with mentors, mentees and parents. No one has reported any concerns. This could potentially be a serious risk given the information shared.

There is a risk that the web-based components (e.g., program website) could be "hacked" and sensitive information accessed. This risk is low given the precautions in place (see below) and has never occurred at NCH.

Cost

Another potential risk is that of cost for those participating in the Mentoring Program. Participants will be reimbursed for data collection, but not for participating in the Mentoring Program itself. Mentors and mentees are expected to have in-person contact, not necessarily engage in activities that incur a cost, but it is possible that they will spend money on activities.

Emotional or physical harm

There is risk for emotional or physical harm for mentees participating in the Mentoring Program. According to Big Brothers Big Sisters, "The rate of reports made to local Big Brothers Big Sisters affiliates for each calendar year from 2000-2010, alleging that anyone within our organization perpetrated child sexual abuse or exploitation on a child associated with our organization, amounts to a fraction of a percentage point per year, based on children served annually. Included in those reports are incidents that may have occurred years or even decades before the report was submitted." Anecdotal reports also suggest that mentoring programs that incur incidents often have not screened mentors appropriately. The likelihood of this risk is probably low, but it is serious.

### 3.0 \* Risk Minimization - Describe procedures for protection against or minimizing potential risks, and assess their likely effectiveness. All proposals should describe steps to be taken to ensure confidentiality regarding the collection, analysis, and storage of data, specimens, etc.:

Confidentiality

Confidentiality is a particular issue for mentoring programs, since mentors and mentees are expected to share personal information. We will regularly highlight its importance: in mentor training, during the mentee/parent orientation that occurs prior to the mentor-mentee introduction, and at each group activity. In both the mentor training and mentee/parent orientation, we will discuss specific confidentiality situations, including communication via the specific types of social media they use, group events, and other situations.

Additionally, confidentiality was a concern for the R21 preceding this proposal. We realized that the likelihood of the risk of disclosure was difficult to determine, so our program coordinator asked about confidentiality concerns during her "check-in" phone calls with mentors, mentees and parents. No one reported any concerns. The program coordinator will continue to ask about confidentiality concerns during "check-in" calls with mentors, mentees and parents, which likely serves as a reminder about confidentiality as well.

The program websites will be accessed via a study-specific password, and NCH has many safeguards in place to protect it from unauthorized access. For example, SSL will be used for encryption, and Apache will be used to protect the site's configuration file and prevent directory browsing. Core system directories will be secured via proper file permissions. Data files, log files and all of the application files will be protected to ensure that they are not readable or writable by unauthorized parties. The application server will reside in the demilitarized zone to add an additional layer of security, and the database server will be hosted behind the NCH firewall.

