**Mentor screening and training:** Mentors will be ≥16 years, ≥1 year post-diagnosis of IBD and managing their IBD well. They will be rigorously screened via an online application, interview, checks of references, driving records and social media, and a background check. They must also successfully complete a 3-hour training conducted by an Investigator and Program Coordinator that includes program policies, relationship development and maintenance, appropriate goals and expectations for the relationship, appropriate roles/boundary issues, self-management, and confidentiality, including limits of confidentiality such as suicidal ideation. All training topics are addressed in the context of mentoring a child with a chronic illness (e.g., understanding limitations in role as mentor, not medical professional), and include role plays with feedback.

**Program support:** Mentors will track contacts with mentees via a private, secure website that was developed for the pilot study. Contact is logged weekly. Mentors will receive regular supervision: Mentors ≤18 years will receive weekly phone supervision for the first month, then twice monthly supervision. Mentors >18 years will receive twice monthly phone supervision for the first 2 months,

then monthly supervision. More frequent supervision will be provided if needed, and the tracking systems will assist in identifying any issues. Supervision will be documented via structured supervision notes. Phone supervision will be provided by Program Coordinators, who will be supervised by study investigators. An "Urgent Response" phone will be staffed at all times by site investigators or Program Coordinators for any situations that might require immediate assistance (e.g., suicidal ideation). Mentees and their parents will be contacted by phone by the Program Coordinator monthly to monitor satisfaction and to address any issues that arise. These phone calls will also be documented. Mentees and parents also have access to the "Urgent Response" phone number.

**Program website:** The private, secure program website includes educational information, a method to contact the study staff, and the aforementioned mentor-contact tracking section through which mentors log contacts with mentees. Each site will have its own program website, hosted by NCH.

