**Parent support:** Parents meet in a support group while the mentors and mentees are engaging in fun activities or while eating lunch before an educational activity. They participate in the educational activities together with the mentors and mentees. Parents also receive monthly phone calls from program staff to address any program-related issues.

**Educational Activity group:** To determine whether peer mentoring is effective, the comparison group consists of 1) educational group events, 2) educational information posted online, and 3) monthly encouragement to engage in activities in the community. The comparison group will participate in the same educational group activities as the mentoring group (separately). Participants also have access to the secure website that has the "Living Well with Inflammatory Bowel Disease: A Self-Management Handbook for Patients and Families with IBD," links to educational videos, and materials from each educational activity. Participants can ask questions about the educational materials on the website, which triggers an email to the program coordinator. To control for some attention aspects of the mentoring program, participants in the comparison group will also be encouraged to engage in activities with a friend at least once a month. Similar to the phone calls that mentees and parents receive each month, comparison youth and parents will receive a monthly phone call encouraging this activity.

**Procedures:** After recruitment, parents and youth will complete measures at baseline. Data will be collected in participants' homes to reduce the number of hospital visits required for families. Then they will be randomized into the mentoring program or comparison group. Youth randomized into the mentoring program will be matched with a mentor, and they will meet each other via a structured introduction. This begins their year-long participation in the program. Youth randomized into the Educational Activity comparison group will be yoked to those in the Mentoring Program so the timing of their educational activities and assessments correspond with their yoked peer.

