(4) Urgent response phone line. A 24-hour "Urgent Response" line will be staffed by the Program Coordinator and Investigators for any participant (mentor, mentee, parent) to call at any time. Program Coordinators will typically have a background in social work and/or counseling and will be trained to manage situations that may arise via the Urgent Response line.

(5) Weekly reporting of mentee contact. Mentors will track the contact they have with their mentees every week via a secure online tracking system. The tracking system is a private section of the program website, making it easy for mentors to track their contact with their mentees. The tracking system consists of drop-down and text boxes in which the mentor describes the date and type of contact (e.g., in person, phone, text), overall rating of the contact, and what activity they participated in if it was an in-person contact. This information is automatically sent as an email to the Program Coordinator. No other mentors see this information. The contact will be monitored daily by the Program Coordinator and discussed with the Investigators in weekly meetings.

(6) Ongoing mentor check-ins. Mentors will receive supervision at least once per month via phone calls by the Program Coordinator which will be discussed with the Investigators in weekly meetings. There will be distinct processes for youth volunteers: Mentors  $\leq 18$  years will receive weekly phone supervision for the first month, then twice monthly supervision. Mentors  $> 18$  years will receive twice monthly phone supervision for the first 2 months, then monthly supervision. More frequent supervision will be provided if needed, for example, if a mentee is shy and the mentor would benefit from additional assistance in working with him or her, or if a family is disorganized and the mentor and mentee family would benefit from problem-solving aimed at developing strategies for scheduling weekly and in-person contact. The need for more frequent supervision will be determined by the Program Coordinator and PI, along with the mentor and/or mentee and family. The online tracking system will assist in identifying any issues. Supervision will be documented via structured supervision notes.

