(7) Ongoing mentee check-ins. Mentees will be called once per month by the Program Coordinator, and these phone calls will be documented and discussed weekly with the Investigators. Mentees will be asked about activities they have participated in with their mentors as well as questions about their relationships with their mentors (e.g., "how are you and your mentor getting along?"). The final broad question is "do you have any (other) concerns?" in case the previous questions have not been sufficient to address any issues. Program Coordinators will have been trained via the Child Welfare Information Gateway publication "What is Child Abuse and Neglect? Recognizing the Signs and Symptoms" to recognize any responses that are concerning and suggest additional follow-up.

(8) Ongoing parent check-ins. Parents will be called once per month by the Program Coordinator,

and these phone calls will be documented and discussed weekly with the Investigators.

(9) Behavioral observation by the Investigators (licensed clinical psychologists) and Program Coordinators of mentor-mentee interactions will occur during the program's educational and recreational group events. Any observations of harm or potential harm (e.g., risky behavior at a recreational event) will be acted on immediately. Observations of interactions that are concerning (e.g., a mentee does not seem comfortable around a mentor) may be addressed at the event and/or addressed via check-in phone calls with the mentor, mentee, and parent, with calls made before regularly scheduled ones as needed.

(10) Specific program policies prohibiting harm are described during training and are listed in the program procedures manuals given to mentors, mentees and parents. Similarly, mentors and mentees are prohibited from being alone together, and must be in the company of others for their in-person get-togethers.

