**3.0 \* Summarize any pre-specified criteria for stopping or changing the study protocol due to safety concerns:**

Stopping or changing the study protocol will be discussed with the investigators and DSMB when/if any adverse events occur.

**4.0 \* Are there any plans to perform an interim efficacy analysis?** Yes  No**If you answered yes, please describe the plans to conduct an interim analysis:****Independent Monitor or DSMB****1.0 \* List the affiliations and qualifications of those monitors who are not associated with the study or describe the composition of the DSMB:**

The study will be monitored by a Data and Safety Monitoring Board (DSMB) comprised of the following members who have accepted positions on the DSMB:

[name], will serve as the Chair of the DSMB. [name] is an expert in the ethics of clinical research and the work of DSMBs. He has served as the Associate Dean for Clinical Research in the College of Medicine and the Director of Regulatory Knowledge and Ethics for the Center for Clinical and Translational Science at the Ohio State University. In these roles, he has provided guidance on a range of issues regarding the ethics of clinical research and the work of DSMBs. He has conducted many clinical trials in the area of HIV.

[name], MSPH, will serve as the Executive Secretary of the DSMB. [name] is a Professor of Pediatric Hematology and the Director of the Center for Clinical Effectiveness Research of the Children's Research Institute at the Medical College of Wisconsin/Children's Hospital of Wisconsin. She has experience with DSMBs, and with her own clinical trials as well as those those conducted in the Center for Clinical Effective Research, which she directs.

[name], ABPP, FAHS, will be the clinical trials expert on the DSMB. He is a Professor in the Department of Pediatrics of the University of Cincinnati, Cincinnati Children's Research Foundation Endowed Chair, and Scientific Director of Clinical Research and Trials at Cincinnati Children's. [name] has conducted multiple clinical trials, the results of which have been frequently cited and published in prestigious journals. He also trains future scientists in the conduct of clinical trials via the training grants he has received and the career development grants his early career mentees have received.

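### As written, confidentiality and other concerns are actively asked about each month only in the mentoring arm, so counts of such concerns by arm would not be comparable

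*Combined protocol and SAP*

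**What the plan says.** **The risk.** Minor Subjects 2.0 justifies the greater-than-minimal-risk classification first by disclosure in groups: "There is a risk of loss of confidentiality, since participants will be engaging in group activities with other participants". Benefits and Risks 2.0 repeats this for participants generally and calls it potentially serious. Methods 1.0 (Educational Activity group) has comparison youth attend the same educational events as the mentoring arm, in separate sessions.

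**The mentoring arm's calls.** Methods 1.0 (Program support) has mentees and their parents "contacted by phone by the Program Coordinator monthly to monitor satisfaction and to address any issues that arise". Benefits and Risks 3.0 adds the confidentiality question: "The program coordinator will continue to ask about confidentiality concerns during 'check-in' calls with mentors, mentees and parents". Item (7) of the same section says "Mentees will be called once per month by the Program Coordinator" and describes questions about the mentor relationship, followed by an open one: "The final broad question is 'do you have any (other) concerns". These calls are documented and discussed with the investigators weekly.

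**The comparison arm's calls.** Methods 1.0 encourages these youth to do something with a friend at least monthly, and then: "comparison youth and parents will receive a monthly phone call encouraging this activity". No other content is stated.

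**The Urgent Response line.** Methods 1.0 (Program support) names mentees and parents as having the number. Benefits and Risks 3.0, item (4), offers it "for any participant (mentor, mentee, parent) to call at any time". Comparison youth are not named in either place.

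**Use of the information.** Data and Safety Monitoring Plan 3.0 says: "Stopping or changing the study protocol will be discussed with the investigators and DSMB when/if any adverse events occur". The DSMB meets within 3 months of the start and then every 6 months, and has unblinded data (Independent Monitor or DSMB 2.0 and 3.0).

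**The concern.** The sponsor gives its own reason for asking: the likelihood of unwanted disclosure was hard to judge beforehand, so the coordinator enquires on calls (Benefits and Risks 2.0 and 3.0). That reason applies equally to a comparison youth who speaks about the disease at a group event. Yet the plan attaches the enquiry to one arm, although a monthly call that could carry it is already made in the other.

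Two things are at stake. First, a disclosure or related distress in a comparison youth depends on someone volunteering it. The pilot's interim study visit has been dropped (Description 2.0), so no formal assessment between baseline and about 12 months makes up for this. Second, adverse events are the only stated trigger for discussing a change or stop. When the DSMB looks at unblinded reports, or a paper lists harms by arm, more reports under mentoring could reflect more events or more questions, and the data could not separate the two.

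**Working it through.** **1. The plan's own figures.** The documents give no rate for confidentiality or other concerns, no capture rate, no adverse-event definition and no between-arm harms analysis, so there is no figure on this point to reproduce. The efficacy power figures (Sample Size Information 2.0) do reproduce. For d = 0.5 and a two-sided 0.05 test (sidedness is assumed), a noncentral t calculation gives 94.0% at 100 per arm and 88.2% at 80 per arm, against the stated 94% and 88%. They play no part in what follows.

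**2. The two arms side by side, as written.**

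| Item | Mentoring | Comparison |
|---|---|---|
| Educational group events | Yes | Yes, held separately |
| Mentor relationship | Yes | None |
| Monthly call to youth and parents | Yes | Yes |
| Confidentiality question on calls | Stated | Not stated |
| Open question on concerns | Stated (mentee calls) | Not stated |
| Documentation and weekly review of calls | Stated | Not stated |
| Urgent Response number | Stated | Unclear |
| Chart review and disease indices | Yes | Yes |

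One point of reading matters. The confidentiality sentence names parents without limiting them to one arm. However, items (3) and (8) of Benefits and Risks 3.0 place parent training and parent check-ins in a list of safeguards for mentee safety once mentors are accepted. The natural reading is parents of mentees. On no reading are comparison youth named.

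Over a 12-month programme with one call a month, the stated enquiries number up to 12 per mentee and none per comparison youth. This counts what the text states, not what coordinators will do.

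**3. Illustration of direction and possible size.** Let p be the true risk of a reportable concern, equal in both arms, and let c_M and c_C be the proportions captured. With 100 youth per arm:

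- expected reports = 100 × p × c
- apparent ratio = (p × c_M) / (p × c_C) = c_M / c_C

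Assumptions not in the documents: p = 5%, c_M = 90%, c_C from 30% to 90%. Mentoring reports are then 100 × 0.05 × 0.90 = 4.5 throughout.

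| c_C | Comparison reports | Apparent ratio |
|---|---|---|
| 30% | 1.5 | 0.90/0.30 = 3.0 |
| 50% | 2.5 | 0.90/0.50 = 1.8 |
| 70% | 3.5 | 0.90/0.70 = 1.29 |
| 90% | 4.5 | 0.90/0.90 = 1.0 |

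The ratio does not depend on p, but its interpretability does. At p = 2% the chance of no reports at all among 100 youth is (1 − 0.02 × 0.90)^100 = 0.16 with 90% capture and (1 − 0.02 × 0.30)^100 = 0.55 with 30% capture. A blank return from an arm that is not asked is therefore weaker reassurance than one from an arm that is.

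**The case against.** The case on the other side is substantial, and much of it stands.

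- **No comparison of harms is planned.** The analysis section covers quality of life, the secondary outcomes, mediation and moderation. The stopping text is triggered by events and sets no rate or ratio between arms. A reader might infer that a planned between-arm harms analysis is biased. The documents contain no such analysis, so the exposure is limited to an informal reading by the DSMB and to any later report by arm.
- **The call scripts are not given.** Methods 1.0 introduces the comparison calls as similar to those made to mentees and parents, and a live call leaves room to volunteer a problem. A reader might infer that comparison youth are never asked, that their harms are missed, or that a breach would stay hidden until the 12-month visit. None of this is shown. Monthly calls and group events continue through the year, and confidentiality reminders are given at group events (Protected Health Information Recording 6.0). Those reminders do not elicit reports, however, and under-detection remains possible.
- **Much of the asymmetry is proportionate.** Emotional or physical harm is described as a risk for mentees, and the signs monitored largely concern mentor conduct and the mentee's response to it. Comparison youth have no mentor, so training and questions on that relationship need no counterpart.
- **Medical events are covered.** Chart review of relapses, hospitalizations and procedures is not limited to one arm and does not depend on the calls.
- **Counts may be near zero.** Asking in the pilot produced no reported concerns, so the DSMB may never see an interpretable ratio. This limits the practical size but does not make the two arms' counts comparable.

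What survives is narrow: a risk shared by both arms is enquired about in only one of them, as the plan is written.

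**Conclusion.** The point holds for confidentiality and other concerns that come to light by asking. For these the plan states no common, arm-neutral way of eliciting reports, so they may be under-detected among the 100 comparison youth and counts by arm would not be comparable. The expected direction is to make mentoring look worse. The size cannot be computed from the documents. The ratios of 1.0 to 3.0 above are assumed capture rates divided by one another, and the distortion vanishes if unprompted capture is as good as prompted capture.

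The conclusion rests on the text as it stands, including the reading that the parents asked about confidentiality are parents of mentees. A comparison-arm script that already contains the same questions would settle the matter. The efficacy analysis, its power and the chart-review outcomes are not affected.

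**What to change.** - In Methods 1.0 (Educational Activity group) and Benefits and Risks 3.0 (Confidentiality, and the mentee and parent check-ins), state that the existing monthly calls to youth and parents in both arms carry the same neutral confidentiality question and the same open question about other concerns. Apply the same documentation and investigator review to both.
- Keep mentor-specific monitoring where it is, but report events found through it separately, so that the DSMB can compare arms on events elicited in the same way.
- Reconcile Methods 1.0 (Program support) with Benefits and Risks 3.0, item (4), on whether the Urgent Response line's reference to any participant includes comparison families.

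The cost is a script and wording change, with no new visits. Calls become slightly longer, and the comparison arm receives a little more attention.
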